Primary study data will be collected both pre-operatively at the patient's initial consultation visit and then again at post-operative visits at 2 weeks, 6 weeks, 3 months, 1 year and 2 years. This study data will include the following: Active peak dorsiflexion of the first MTP joint, SF-36 score, Visual analog pain score (VAS) and FAAM. This will be recorded on the attached Data Collection Form at each visit. The VAS will be performed by providing patient's with a 10 cm line and having them mark on the line where they would rate their daily pain in their 1st MTP joint. That distance from the beginning of the line will then be measured in millimeters to identify the patient's VAS score. The patient's active peak dorsiflexion will be measured in clinic with a goniometer with the patient standing and weight bearing on their operative foot. The Medical Outcomes study Short form (SF-36) has been validated and thoroughly tested for a wide range of medical conditions, including ankle arthritis, to monitor patient symptoms and responses to treatment. The questionnaire focuses on both the mental and physical aspects of a certain condition to generate composite score. The score provides the opportunity to compare patient outcomes prior to and following their surgical intervention, as well as track their progress throughout the recovery process. Finally, the Foot and Ankle Ability Measures (FAAM) questionnaire will be collected at the above stated time points. This measure has been validated for subjects with foot and ankle musculoskeletal disorders. It has also been shown to be more responsive to changes in physical functioning than the SF-36 score. At each follow up visit, the patient will be evaluated for any adverse events. If an adverse event is identified, an adverse event form (attached) will be completed. All of the above will apply to the 2 week visit, except for the administration of questionnaires/surveys. Additionally, subjects will have incision check, suture removal, and a physical completed during this visit.

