#### **Data Safety and Monitoring Plan:**

As seen in previous literature, both the Cheilectomy and Cartiva hemiarthroplasty procedures are relatively low risk. Furthermore, both procedures are indicated for patients with Grade 2 Hallux Rigidus. In the study done by Baumhauer et al, 9% of patients in the Cartiva group required implant removal and revision to a MTP joint fusion. All cases were due to persistent pain following Cartiva implant, with no evidence of significant bone loss or implant wear. Additionally, all cases of revision were successfully revised to an arthrodesis without complication. Additionally, there is an estimated 8-10% revision rate following Cheilectomy, with revision to arthrodesis being the common procedure. For this study, the primary surgeons will use their clinical judgement to determine if a patient will require a revision procedure if they have persistent pain following their initial surgery.

[name], surgical resident in the Department of Orthopedic Surgery will be responsible for the monitoring of this data, under supervision from the PI, [name]. We plan to assess our data and do a primary study evaluation when our enrollment has reached 25% of our stated enrollment goal. Unanticipated problems, adverse events, protocol deviations and violations will be reported to the IRB within 14 days following.

If, at the point of initial evaluation (25% of targeted enrollment), there is a higher than expected complication rate in either treatment arm, the study will be postponed at that time for further evaluation and possible discontinuation.

In the case that our initial evaluation shows negative results and occurs prior to a continuing review, we will contact the IRB with the information and seek to reevaluate or possible discontinue the study. All study team members have completed relevant training materials, are well versed in maintaining clinical integrity and data validity, and will be formally instructed in the

proper application of this protocol. Data/images will be evaluated by the PI, [name], as well as [name] and [name], study team members. This data will be passed to [name], whereupon it will be stored securely as outlined in the Data and Record Keeping section of our protocol."

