### **Statistical Considerations:**

The primary hypothesis of the study is to show that long term (2 year) functional outcomes for those undergoing Cartiva are no worse than the long term functional outcomes for those undergoing Cheilectomy. The primary outcome is the FAAM – ADL subscore from baseline to 2 years post-surgery. The MCID of FAAM-ADL is 8 units and we assume the SD of the difference in FAAM – ADL from baseline to 2 years post-surgery is near 17 units. To have 80% power in a non-inferiority test under these assumptions, we would need to recruit 57 subjects per group. For those subjects that are lost-to-follow-up or have a subsequent surgery we will impute the missing 2 year follow-up value in two ways: 1) by LOCF (last observation carried forward) and 2) by mean 2 year follow-up value for those in the same surgical group. We will then examine results from both method as a sensitivity analysis of our imputation method. To further assist in ensuring enough patients in each group we will inflate our sample size to 60 per group for a total of 120 patients.

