Primary analyses will follow the ITT principle and be based on changes in outcomes from baseline to 2 years follow-up between the two randomized groups. Statistical testing for primary analyses will consist of non-inferiority t-tests between the two groups for each numerical outcome. Secondary analyses will consist of similar non-inferiority t-tests between the two groups but at differing follow-up time points (i.e. 3 months, 6 months, and 12 months). Rates of secondary surgeries will be estimated for each group and 95% Cis will be calculated. Exploratory comparison analyses, including RM-ANOVA and log-rank survival analysis, will be examined as well to see if there were statistical differences in the various outcomes between groups. These analyses methods will be applied similarly to the secondary outcomes as well. For each patient reported outcome measure, we will use the Minimal clinically important difference (MCID) for each measure. As described above, the MCID for the FAAM-ADL subscore is 8 units. The MCID for the FAAM-Sports subscore is 9 units. The MCID for the SF-36 Physical component is estimated at 2 units for patients with lower extremity osteoarthritis conditions. The MCID for the VAS was found to be - 8 mm when evaluating patients with foot pain. Using these values, we will evaluate non-inferiority by comparing the changes from pre-operative results to the results at the described time points. Non-inferiority will be defined as differences that are less than the MCID between the Cartiva and Cheilectomy groups. Furthermore, we will assess whether patient characteristics affected the functional results between the two surgical groups by including a patient characteristic by group interaction into the statistical models.

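### The primary t-test on change could be replaced by ANCOVA on baseline FAAM-ADL, with the same difference, the same 8-unit margin and possibly more power, provided group-mean imputed values are not analysed as observed

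*Combined protocol and SAP*

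**What the plan says.** All of the design statements are in the Statistical Considerations section. The endpoint is defined as follows: "The primary outcome is the FAAM – ADL subscore from baseline to 2 years post-surgery". For the sample size, "we assume the SD of the difference in FAAM – ADL from baseline to 2 years post-surgery is near 17 units". The margin is the FAAM-ADL MCID of 8 units, and 57 per group are planned for 80% power, raised to 60. The analysis is ITT on change from baseline: "Statistical testing for primary analyses will consist of non-inferiority t-tests between the two groups for each numerical outcome". No baseline covariate is named. RM-ANOVA is exploratory, and patient characteristics enter only as interactions with group.

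For patients who are "lost-to-follow-up or have a subsequent surgery we will impute the missing 2 year follow-up value in two ways", the two ways are LOCF and imputation "by mean 2 year follow-up value for those in the same surgical group". Neither is named as the deciding one.

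On baseline data, Research Designs and Methods states: "Primary study data will be collected both pre-operatively at the patient's initial consultation visit and then again at post-operative visits". The Data Collection Form has a FAAM-ADL field and a pre-operative option. The visit table in the same section has no mark for that form at Screening, but the planned change score needs the same value.

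**The concern.** A change score forces the slope of the 2-year score on baseline to be exactly 1. If the true slope differs, variance that baseline could explain stays in the error term. The trial already holds the baseline value, so the plan passes up precision that would need no new data.

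The power reserve is thin. Going from 57 to 60 covers only 5% loss (57/60 = 0.95). The Data Safety and Monitoring Plan reports from an earlier trial that "9% of patients in the Cartiva group required implant removal and revision to a MTP joint fusion", and "there is an estimated 8-10% revision rate following Cheilectomy". Applied to 60 per group, that is 5.4 patients plus 4.8 to 6.0, or 10.2 to 11.4 of 120 (8.5% to 9.5%). These patients' 2-year values would go to imputation before any loss to follow-up.

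The same rule creates a hazard. Values set to the group mean and analysed as observed make the standard error too small. In a non-inferiority trial this means declaring Cartiva non-inferior too often, and the effect is stronger under ANCOVA.

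**Working it through.** **Inputs.** From Statistical Considerations: margin 8, SD of change 17, 60 per group. Not stated and therefore assumed: one-sided alpha 0.05, true difference 0, correlation rho between baseline and 2-year scores of 0.3 to 0.7, and ratio k = SD(2 years)/SD(baseline) of 0.7 to 1.3.

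**The plan's own figure.** Noncentral-t power of the change-score test at one-sided 0.05 is 79.7% at 56 per group, 80.3% at 57 and 82.1% at 60, so 57 is reproduced. At one-sided 0.025, 72 per group would be needed. One-sided 0.05 is therefore the alpha that fits.

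**Variance comparison.** Let s0 be the baseline SD.
- Var(change) = s0²(1 + k² − 2·rho·k) = 17².
- ANCOVA residual variance = k²·s0²(1 − rho²).
- The first minus the second is s0²(rho·k − 1)². This is never negative and is zero only when the slope rho·k equals 1.

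Because of randomization, both analyses estimate the same between-group difference with complete data, so the margin carries over.

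**Equal SDs (k = 1).** The residual SD is 17·√((1 + rho)/2). The standard error of the difference is SD·√(2/60).

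| Analysis | Residual SD | SE | 8/SE | Power at 60 per group | n per group for 80% |
|---|---|---|---|---|---|
| t-test on change | 17.0 | 3.10 | 2.58 | 82.1% | 57 |
| ANCOVA, rho 0.3 | 13.7 | 2.50 | 3.20 | 93.7% | 37 |
| ANCOVA, rho 0.5 | 14.7 | 2.69 | 2.98 | 90.6% | 43 |
| ANCOVA, rho 0.7 | 15.7 | 2.86 | 2.80 | 87.2% | 49 |

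A small-sample factor of 1 + 1/116 on the variance changes the ANCOVA powers to 93.6%, 90.3% and 86.9%. At one-sided 0.025 the t-test has 72.5%, and ANCOVA has 88.7%, 83.9% and 79.2%.

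**Unequal SDs.**
- k = 0.7, rho = 0.3: variance ratio 0.49·0.91/1.07 = 0.417, power 99.0%.
- k = 1.3, rho = 0.7: variance ratio 1.69·0.51/0.87 = 0.991, power 82.4%, so almost no gain.
- Slope exactly 1, with the small-sample factor: 81.8%, a cost of 0.3 points.

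**Missing 2-year values.** Simulation with 20,000 trials per setting, k = 1, rho 0.3 to 0.7, one-sided 0.05, values missing completely at random. Type I error is taken at a true difference of −8. The observed-case t-test powers are noncentral-t values at 54 and 48 per group.

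| | 10% missing | 20% missing |
|---|---|---|
| Type I: t-test, group mean entered as observed | 5.8–6.0% | 6.9–7.1% |
| Type I: ANCOVA, group mean entered as observed | 6.9–7.0% | 9.4–9.7% |
| Type I: ANCOVA, multiple imputation from baseline | 4.9–5.0% | 4.7–4.9% |
| Power: ANCOVA, multiple imputation, rho 0.3/0.5/0.7 | 91.0/86.9/83.2% | 87.5/82.5/78.8% |
| Power: t-test on observed cases | 78.4% | 74.0% |

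A separate simulation with 8,000 trials per setting agrees: ANCOVA with group means gave 7.1–7.6% and 9.2–9.3%, and the t-test 6.0–6.2% and 6.7–7.3%.

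The mechanism shows at rho 0.5 with 20% imputed. For ANCOVA the average reported SE is 2.49, below the complete-data 2.69, while the true spread of the estimate is 3.14. For the t-test the reported SE is 3.10 and the true spread 3.48. An imputed change score still varies through the patient's own baseline, but an imputed 2-year score does not vary within its group.

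**The case against.** The strongest reply is that nothing is broken. On the inferred alpha the planned test is valid with complete data and already exceeds 80% power at 60 per group. The gain depends on a correlation and SDs that the documents do not give; at k = 1.5 and rho = 0.7, ANCOVA has 82.1%, which is no gain. All of this stands, and it limits the claim to a possible gain.

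A second reply is that group-mean imputation is a flaw under either model and belongs elsewhere. It does affect both, but more under ANCOVA. Recommending the model without that condition would raise the false non-inferiority rate. The inflation figures apply only if group-mean imputation decides the result, which the plan leaves open.

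A third reply is that the missing values will not be random. The Data Safety and Monitoring Plan attributes the earlier Cartiva revisions to persistent pain. With missingness favouring worse change, rho 0.5 and assumed missing rates of 15% for Cartiva and 8% for cheilectomy, observed-case ANCOVA has a type I error of about 11%. This limitation stands, and multiple imputation from baseline alone rests on a similar assumption. It is no reason to prefer the t-test, which in the same setting had 12.7% against 11.3% for ANCOVA.

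Three smaller points also stand. Background and Significance gives a 5% Cartiva revision rate at 5 years, so the share imputed could be lower. The observed-case t-test is not the planned analysis. Observed-case ANCOVA has 83.9–91.0% power with 10% missing and 79.3–88.1% with 20%, so the power gain comes from the baseline adjustment and not from multiple imputation.

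**Conclusion.** The point holds as an improvement to consider. ANCOVA on baseline FAAM-ADL answers the same question against the same margin. With complete data it costs at most about 0.3 points of power and may add about 5 to 12 points if the SDs are equal and rho lies between 0.3 and 0.7. Over the wider assumed range, ANCOVA power runs from 82.4% to 99.0%, against 82.1% for the t-test.

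The direction is secure and the size is not, because rho, the separate SDs and alpha are unstated. The missing-data figures assume values missing completely at random, so they show direction and rough size only. LOCF was not quantified.

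**What to change.** Pre-specify, before outcomes are seen:

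- **Primary model:** ANCOVA of the 2-year FAAM-ADL score on treatment and baseline FAAM-ADL. Judge non-inferiority from the confidence bound of the adjusted difference (Cartiva minus cheilectomy) against the 8-unit margin, at a stated alpha.
- **Missing 2-year values:** a method that carries the imputation uncertainty, such as multiple imputation by group using baseline and interim scores. Keep LOCF and group-mean imputation as sensitivity analyses only.
- **Supporting analysis:** the t-test on change.
- **Other outcomes:** the same adjustment for FAAM-Sports, the SF-36 physical component and VAS, which have stated margins. Peak dorsiflexion has none, and ANCOVA does not cure that.
- **Visit table:** mark the Data Collection Form at Screening, to match the text.

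The cost is SAP wording, one degree of freedom and slightly more analysis work, with no new data. If the true slope is 1, the power cost is about 0.3 points with complete data. With 10% to 20% missing and multiple imputation it is about 1 point against the observed-case t-test (78.0% against 78.7%, and 72.6% against 73.7%, in simulation). Changing the model while still entering group means as observed would bring a false non-inferiority rate of about 7% with 10% imputed and about 9.5% with 20%.

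### The exploratory RM-ANOVA has no rule for missed interim visits: a classical fit would drop those patients, whereas a mixed model would use every observed score

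*Combined protocol and SAP*

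**What the plan says.** All the analysis text is in the combined protocol and SAP, under Statistical Considerations.

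- **Longitudinal comparison.** One sentence covers it: "Exploratory comparison analyses, including RM-ANOVA and log-rank survival analysis, will be examined as well". No model form, covariance structure, list of visits or rule for a missed visit follows. The same methods are to be applied to the secondary outcomes.
- **Imputation.** For patients lost to follow-up or with a further operation, "we will impute the missing 2 year follow-up value in two ways": by LOCF, and "by mean 2 year follow-up value for those in the same surgical group". Nothing is said about a missing 6-week, 3-month or 1-year score.
- **Primary analysis.** "Statistical testing for primary analyses will consist of non-inferiority t-tests between the two groups for each numerical outcome", on change from baseline to 2 years. The ITT sentence is attached to these primary analyses. Secondary t-tests at earlier time points, including 3 and 12 months, are planned separately.
- **Visits.** Research Designs and Methods schedules "post-operative visits at 2 weeks, 6 weeks, 3 months, 1 year and 2 years". It then says "All of the above will apply to the 2 week visit, except for the administration of questionnaires/surveys". The questionnaires therefore have four post-operative occasions: 6 weeks, 3 months, 1 year and 2 years.

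**The concern.** Classical RM-ANOVA needs a complete row of scores for each patient, and the stated imputation does not supply one. A patient who misses only the 6-week form would be dropped along with three observed scores. A patient lost before the 1-year visit would receive an imputed 2-year value, still have a blank at 1 year, and also be dropped. The uncorrected univariate test further assumes sphericity, which is doubtful for visits spaced from 6 weeks to 2 years.

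What is at stake is the description of recovery in each arm. It could rest on fewer patients than were randomised, and on those who attended most reliably. Because the methods carry over to the secondary outcomes, the same holds for FAAM-Sports, SF-36, VAS and dorsiflexion. Dorsiflexion is also measured at 2 weeks, so it has one more occasion to miss.

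**Working it through.** **1. The plan's own figure.** There is no stated figure for missed visits. The nearest is the sample size of 57 per group. Inputs: margin 8 units ("Non-inferiority will be defined as differences that are less than the MCID between the Cartiva and Cheilectomy groups", with an MCID of 8 for FAAM-ADL), SD 17 ("2 years post-surgery is near 17 units"), power 80%, true difference 0.

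n per group = 2 × SD² × (z_α + z_β)² / margin². With one-sided α = 0.05 (not stated in the plan): 2 × 289 × (1.645 + 0.842)² / 64 = 55.8, so 56. The noncentral t calculation gives 57 (power 0.803), which matches. One-sided 0.025 gives 72. RM-ANOVA plays no part in this calculation, so the point below leaves it untouched.

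**2. Patients kept by a complete-case fit.** Inputs: 120 patients (60 per group, Statistical Considerations), baseline present for all (assumed), and a missing rate q at each visit, independent across visits (assumed; the documents give none). The plan does not say whether the imputed 2-year value enters RM-ANOVA, so both cases are shown.

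- Imputed value enters, three visits exposed: 120 × (1 − q)³
- Imputed value does not enter, four visits exposed: 120 × (1 − q)⁴

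| q | 2-year value imputed | Not imputed |
|---|---|---|
| 3% | 120 × 0.913 = 110 | 120 × 0.885 = 106 |
| 5% | 120 × 0.857 = 103 | 120 × 0.815 = 98 |
| 10% | 120 × 0.729 = 87 | 120 × 0.656 = 79 |
| 15% | 120 × 0.614 = 74 | 120 × 0.522 = 63 |

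**3. Observed scores discarded.** Observed post-operative scores number 480 × (1 − q), since 120 × 4 = 480.

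- With the 2-year value imputed, the scores kept are 120 × (1 − q)³ × (4 − q). At q = 10% that is 341 of 432, so 21% are discarded. At 5% it is 11%, and at 15% it is 30%.
- Without imputation, the scores kept are 480 × (1 − q)⁴. The discarded shares are 14%, 27% and 39% at 5%, 10% and 15%.
- A likelihood-based mixed model uses all the observed scores: 456, 432 or 408 of 480.

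**4. Clustering.** If the same patients miss every visit, the number kept is 120 × (1 − q), which is 108 at q = 10%. At that rate the range therefore runs from 79 (independent, not imputed) to 108 (fully clustered).

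**The case against.** The case for leaving the text alone is substantial, and much of it stands.

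- **The analysis is exploratory.** The non-inferiority conclusion comes from the 2-year t-test. This stands, and it limits the importance of the point.
- **Interim scores are used elsewhere.** The 3- and 12-month t-tests can include a patient who missed some other visit. This stands too; only the 6-week scores have no by-visit test of their own.
- **Listwise deletion and sphericity belong to the classical fit.** The label RM-ANOVA is sometimes used for a mixed model. Sphericity corrections or the multivariate form avoid the second problem, and the plan excludes none of these. A reader might infer that patients will certainly be dropped. The documents do not say so, because they do not say how the model is fitted. That gap is itself the reason to edit.
- **Interim attendance may be good.** Research Designs and Methods calls the visits through 1 year standard of care and excludes people who cannot commit to follow-up. This favours the lower rates in the table, but it gives no rate and no rule for the forms that are missed.
- **A mixed model does not cure informative missingness.** This is correct: it relies on missing at random. It still uses the observed scores of patients with gaps, which a complete-case fit throws away.

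**Conclusion.** The point holds in a limited form. RM-ANOVA is the only method named for comparing scores across visits, imputation stops at the 2-year value, and no rule covers a missed interim visit. Under a classical fit, with 5% to 15% independent missingness per visit, between 103 and 74 of 120 patients remain if the imputed 2-year value is used, and between 98 and 63 if it is not. Clustering of missed visits would raise these counts. The rates and the independence are assumptions, so none of these figures is a forecast.

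Three stronger readings are tempting, and the documents do not support them:

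- **A broken ITT commitment.** The ITT sentence covers the primary analyses only. An exploratory complete-case fit would move away from the randomised population without contradicting the plan.
- **A threat to the main result.** The 2-year t-test, the sample size and the 3- and 12-month t-tests do not depend on RM-ANOVA.
- **A subgroup objective that rests on RM-ANOVA.** The characteristic-by-group interaction is promised for unnamed statistical models, so this would be a guess.

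This is an inexpensive improvement to an underspecified exploratory analysis. It is not a defect in the primary one.

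**What to change.** In Statistical Considerations, replace RM-ANOVA with a mixed model for repeated measures on change from baseline:

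- Fixed effects for arm, visit, arm-by-visit and baseline score, with an unstructured covariance. Four questionnaire visits need 4 × 5 / 2 = 10 covariance parameters.
- All observed scores enter. Interim gaps are not imputed, and the 2-year imputed values are kept out of this model.
- The arm difference is reported with a confidence interval at each scheduled visit.
- The 2-year FAAM-ADL contrast is set against the 8-unit margin, at the same significance level as the primary test, and reported beside the LOCF and group-mean results. It gives a check that depends on neither filling method.
- The text states that the model assumes missing at random, and how scores after a subsequent surgery enter it. The Data Safety and Monitoring Plan cites revision in 9% of Cartiva patients in an earlier trial and 8–10% after cheilectomy, so the rule will affect real data.

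The cost is SAP wording and a little more analysis work. No new visits, patients or data are needed, and standard software fits the model.
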